8.2 SAFETY AND OTHER ASSESSMENTS

SPIRIT is a one-time psychoeducational intervention. The proposed trial involves very minimal or low risk. Patient and surrogate participants may experience an emotional reaction (e.g., anxiety). However, in our previous studies,¹⁷⁻²⁰ intervention dyads were less apprehensive and more satisfied with the quality of communication than control dyads. It is expected that psychological burden caused by the SPIRIT intervention will be less than or equal to that of usual care.

8.3 ADVERSE EVENTS AND SERIOUS ADVERSE EVENTS

8.3.1 DEFINITION OF ADVERSE EVENTS (AE)

SPIRIT is a one-time psychoeducational intervention. The study involves very low risk and the potential risk may include emotional upset during the session, which is not a “medical occurrence”. SPIRIT has been extensively tested in previous trials and no safety concerns have ever arisen.

8.3.2 DEFINITION OF SERIOUS ADVERSE EVENTS (SAE)

SPIRIT is an advance care planning intervention to prepare these patients and their surrogates for end-of-life decision making. SPIRIT’s safety and beneficial effects (e.g., reducing psychological distress) have been consistently demonstrated. Participants’ deaths or hospitalizations, if any, during the trial will occur as part of the illness course and will extremely unlikely be related to the intervention or any study related procedures. However, any participant’s death will be reported to IRB through annual progress report and included in the NIH annual progress report.

8.3.3 CLASSIFICATION OF AN ADVERSE EVENT

8.3.3.1 SEVERITY OF EVENT

Not applicable.

8.3.3.2 RELATIONSHIP TO STUDY INTERVENTION

Not applicable.

8.3.3.3 EXPECTEDNESS

There are no known expected adverse reactions. SPIRIT has been tested in 5 RCTs with various patient populations with serious chronic conditions and in different U.S. regions and settings. Although possible adverse reactions to the intervention may include emotional distress during the intervention session, no such reactions have been observed in the previous studies. Thus, these reactions are very unlikely to occur. However, intervention sessions will stop if the participant appears to be emotionally distressed, and a break or rescheduling will be offered.

8.3.4 TIME PERIOD AND FREQUENCY FOR EVENT ASSESSMENT AND FOLLOW-UP

Not applicable.

8.3.5 ADVERSE EVENT REPORTING

The possible adverse reactions, such as emotional distress during the intervention session, if ever occurs, will be tracked (documented in the study REDCap) and the aggregated numbers will be reported at the upcoming biannual DSMC meeting.

Between the post-intervention (or post-randomization for the usual care group) follow-up and the 12-month follow-up with selected surrogates, there will be no study procedures that are required for participants other than our monthly check-in calls and there will be no data collection involved. Thus, the study team will have no way of knowing if there are any disease-related events (DREs) in the study population. **However, any participant's death, if known, will be reported to IRB through annual progress report and included in the NIH annual progress report.**

8.3.6 SERIOUS ADVERSE EVENT REPORTING

Not applicable.

8.3.7 REPORTING EVENTS TO PARTICIPANTS

Not applicable.

8.3.8 EVENTS OF SPECIAL INTEREST

Not applicable.

8.3.9 REPORTING OF PREGNANCY

Not applicable.

8.4 UNANTICIPATED PROBLEMS

8.4.1 DEFINITION OF UNANTICIPATED PROBLEMS (UP)

Unanticipated problems are defined by DHHS 45 CFR part 46 as any incident, experience, or outcome that meets all of the following criteria:

- unexpected, in terms of nature, severity, or frequency, given (a) the research procedures that are described in the protocol-related documents, such as the IRB-approved research protocol and informed consent document; and (b) the characteristics of the study population;
- related or possibly related to participation in the research (in this guidance document, possibly related means there is a reasonable possibility that the incident, experience, or outcome may have been caused by the procedures involved in the research);
- suggests that the research places participants or others at a greater risk of harm (including physical, psychological, economic, or social harm) than was previously known or recognized.

It will be extremely unlikely in this study that the events of fatigue or emotional distress would meet the all of the criteria above.

8.4.2 UNANTICIPATED PROBLEM REPORTING

If we encounter any adverse event that meets the definition above and that is related to the intervention, the PI will notify the Emory IRB and NINR Program Official and the DSMC within 24 hours of the event being reported to the PI. The expedited report will be followed by a detailed, written SAE report as soon as possible.

8.4.3 REPORTING UNANTICIPATED PROBLEMS TO PARTICIPANTS

Not applicable.

9 STATISTICAL CONSIDERATIONS

9.1 STATISTICAL HYPOTHESES

In Stage 1A, SPIRIT will be tested with the first 10 dyads. Based on the inputs from the first 10 dyads, SPIRIT will be modified and then tested with another 10 dyads. The purpose of this pretesting is to adapt SPIRIT for the target population and test the study procedures. Therefore, there will be no hypotheses to be tested.

In Stage 1B,

- Primary Endpoint(s):
 - 1) The number of intervention dyads who are congruent on goals of care at post-intervention will be significantly higher than that of control dyads.
 - 2) Surrogate decision making confidence (DMC) in the intervention group at post intervention will be significantly higher than those of control dyads.
 - 3) Surrogate preparedness scores in the intervention group at post intervention will be significantly higher than those of control surrogates.

9.2 SAMPLE SIZE DETERMINATION

Our sample size of 40 dyads per group in Stage 1B can detect preliminary efficacy of SPIRIT-in person or SPIRIT-remote (compared to usual care) on two preparedness outcomes based on effect sizes of the SPIRIT intervention in our previous studies.^{27-30,32} For dyad congruence, we observed large effect sizes ($OR=4.4-8.7$) at 1 or 2 weeks post intervention,^{28,32} which would require only 10-20 dyads/group to achieve over 80% power. For surrogate DMC, a sizable treatment effect was observed at 2 months post intervention,³⁰ but at short-term (2 weeks), the effect size was negligible (Cohen's $d=.02$).³² Therefore we plan to carefully investigate trends and obtain an estimate of the effect size for the AD population instead of solely focusing on hypothesis testing.

Revised sample size calculations (with V12): Due to changes in the study design, we revised our sample size calculation. In particular, the new study design will use 2 parallel RCTs: (1) A 3-arm (SPIRIT-in person, SPIRIT-remote and usual care) RCT for dyads residing in Atlanta and vicinities (within ~40 miles from Emory), and (2) a 2-arm (SPIRIT-remote and usual care) RCT if the dyad resides in an area outside of the perimeter. Effect sizes estimates, corresponding to the preparedness outcomes from PI's previous studies, formed the basis for power calculation.^{27-30,32} For dyad congruence, we previously observed large effect sizes ($OR=4.4-8.7$) at 1 or 2 weeks

post intervention,^{28,32} which would require only 10-20 dyads/group to achieve over 80% power. For surrogate DMC, a sizable treatment effect was observed at 2 months post intervention,³⁰ but at short-term (2 weeks), the effect size was negligible (Cohen's $d=.02$).³²

Based on the updated design, we are targeting $n=48$ dyads for the 3-arm RCT and $n=72$ dyads for the 2-arm RCT to meet our overall target of $N=120$ dyads. While we are still adequately powered to detect differences in dyad congruence in the standalone RCTs; However, for the surrogate DMC outcome, our goal will be to estimate the population parameters or effect sizes and investigate trends. In addition, effect sizes from both RCTs will be pooled, whenever appropriate, to improve power.

Revised sample size calculation with V14: In light of the changes in study design, we revised our sample size calculation. Moving forward, the new study design will only use a 2-arm (SPIRIT-remote and usual care) RCT for all dyads included in the study based on 3 sites, both within and outside Georgia. Effect sizes estimates, corresponding to the preparedness outcomes from the previous studies, formed the basis for power calculation.^{27-30,32} For dyad congruence, we previously observed large effect sizes ($OR=4.4-8.7$) at 1 or 2 weeks post intervention^{28,32}. We found that a total sample size of 72 obtained by sampling subjects from 3 sites with an average of 12 dyads per group (24 total from each site) will achieve adequate ($>80\%$) power to detect the smallest effect size (odds ratio of 4.3). Because the effect size was negligible for surrogate DMC (Cohen's $d=.02$).³², our goal will be to establish the population parameters. Considering attrition, the target sample size of 120 dyads will achieve sufficient power.

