9.4.2 ANALYSIS OF THE PRIMARY ENDPOINT(S)

SPIRIT effects on the preparedness outcomes: For dyad congruence, a binary outcome (congruent or not congruent), a generalized mixed effects logistic regression model will be used. Specifically, a random intercept model will be used to account for dyad level variation over time while treatment group, time (baseline and post-intervention), and treatment x time interaction will be treated as fixed effects. If there is a significant treatment x time interaction ($\alpha<0.05$) (an overall treatment effect), then two contrasts will be tested for individual treatment effectiveness (usual care vs SPIRIT-in person and usual care vs SPIRIT-remote). Adjustments for multiple pairwise comparisons will be made using Tukey's test. Surrogate DMC and preparedness scores, we will use linear mixed

effects regression models, adjusting for potential covariates as appropriate. Since this is not a non-inferiority trial where two or more interventions that have been proven to be superior to usual care are being compared, the contrast, SPIRIT-in person vs SPIRIT-remote, cannot be tested. However, if superiority of the two modalities to usual care is determined, the estimated group differences could be used for selecting a non-inferiority margin or equivalence range^{124,125} for future studies.

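### Section 9.2 still says that OR 4.4-8.7 needs only 10-20 dyads per group for over 80% power on dyad congruence; at OR 4.4, 20 per group gives at most 62%, and the V14 figure omits the control rate it depends on

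*Combined protocol and SAP*

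**What the plan says.** Section 9.2 of the combined protocol and SAP holds three sample-size calculations in sequence: the original one, a V12 revision and a V14 revision.

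- **Original.** The effect size comes from earlier trials: "For dyad congruence, we observed large effect sizes ($OR=4.4-8.7$) at 1 or 2 weeks". This is followed by "which would require only 10-20 dyads/group to achieve over 80% power". The planned size was 40 dyads per group.
- **V12.** The same odds ratios and the same 10-20 claim are repeated. The design becomes a 3-arm trial with 48 dyads and a 2-arm trial with 72. The paragraph asserts: "While we are still adequately powered to detect differences in dyad congruence in the standalone RCTs".
- **V14.** The design becomes one 2-arm trial of SPIRIT-remote against usual care. The odds-ratio range is repeated without the 10-20 claim. The calculation now uses "a total sample size of 72 obtained by sampling subjects from 3 sites with an average of 12 dyads per group", which "will achieve adequate ($>80\%$) power to detect the smallest effect size (odds ratio of 4.3"). The 120-dyad target is then called sufficient after attrition.

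Section 9.2 gives no control-group congruence rate, alpha, sidedness, test or attrition rate for any of these figures.

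**The concern.** Dyad congruence is the first primary endpoint in section 9.1 and the only one for which the plan claims power. For surrogate confidence it expects a negligible short-term effect and aims only to estimate it.

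Two things looked wrong. The claim of 10-20 per group for OR 4.4 sits a paragraph or two above a V14 calculation that uses 36 per group for the almost identical OR 4.3. And no power figure for a binary endpoint can be checked without the control rate, which the section never states. At stake is whether the power statements in the current text can be relied on or cited, for example when planning a later trial from this pilot.

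**Working it through.** **Inputs**

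- Odds ratios: 4.4 and 8.7 (section 9.2, original and V12) and 4.3 (V14).
- Dyads per group: 10 and 20 as stated; V12 3-arm trial 48/3 = 16; V14 3 sites × 12 = 36; full target 120/2 = 60.
- Alpha: 0.05, taken from section 9.4.2 ("If there is a significant treatment x time interaction ($\alpha<0.05"). Sidedness is not stated. The hypothesis in section 9.1 is directional ("will be significantly higher than that of control dyads"), so one-sided results are shown as well.
- Control congruence p0: not in the documents. It is scanned. A maximum over all p0 needs no assumption; ranges quoted for 10-60% or 10-70% do.
- Attrition: none in section 9.2. I assume 3.8%, the dropout of the earlier efficacy trial cited in section 5.5: 60 × 0.962 = 57.7, taken as 57 per group.

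**Formulas** (1:1 allocation, pooled two-proportion test)

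- p1 = OR·p0 / (1 − p0 + OR·p0), and m = (p0 + p1)/2
- n = [1.96·√(2m(1−m)) + 0.8416·√(p0(1−p0) + p1(1−p1))]² / (p1 − p0)²
- power = Φ{ [(p1 − p0)·√n − 1.96·√(2m(1−m))] / √(p0(1−p0) + p1(1−p1)) }

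**Step 1: the plan's 10-20 per group.** For OR 4.4 the most favourable control rate is about 0.32. Then p1 = 1.408/2.088 = 0.674, m = 0.497, and the difference is 0.354.

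- Required n = (1.96 × 0.7071 + 0.8416 × 0.6612)² / 0.354² = 30.05, so 31. An exact chi-square test just reaches 80% with 30.
- Power at n = 20: (0.3543 × 4.472 − 1.386)/0.6612 = 0.30, and Φ(0.30) = 0.62.

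The same scan for each stated pair gives:

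| OR | n per group | Highest power at any control rate | Control rates giving over 80% |
|---|---|---|---|
| 4.4 | 10 | 34% | none |
| 4.4 | 16 | 52% | none |
| 4.4 | 20 | 62% (74% one-sided) | none |
| 8.7 | 10 | 61% (74% one-sided) | none |
| 8.7 | 20 | 91% | about 10.5-50.5% |

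Dyads per group needed for 80% power, two-sided:

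| Control rate | 10% | 20% | 30% | 40% | 50% | 60% |
|---|---|---|---|---|---|---|
| OR 4.4 | 50 | 34 | 31 | 31 | 35 | 42 |
| OR 8.7 | 21 | 16 | 16 | 17 | 20 | 25 |

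The minimum for OR 8.7 is 14.9, so 15, at a control rate near 25%. So 10-20 is replaced by about 31-50 for OR 4.4 and 15-25 for OR 8.7.

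**Step 2: a possible origin.** Converting the odds ratio to Cohen's d as ln(OR)·√3/π gives 0.817 and 1.193. A one-sided t-test then needs 19.3 and 9.5 per group, which is 10-20. The plan does not say that this was done. It treats a binary endpoint as continuous, and two-sided it needs 25 and 13.

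**Step 3: V12's standalone trials.** The 3-arm trial has 16 per arm: at most 52% at OR 4.4 (54% with an exact test at the best control rate), before any Tukey adjustment. The 2-arm trial has 72/2 = 36 per group, so its adequacy depends on the control rate in the same way as V14's figure.

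**Step 4: V14 at OR 4.3.**

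| Control rate | 10% | 20% | 30% | 40% | 50% | 60% | 70% |
|---|---|---|---|---|---|---|---|
| Power, 36 per group | 65% | 82% | 86% | 85% | 81% | 73% | 61% |
| Power, 57 per group | 84% | 95% | 97% | 97% | 95% | 90% | 81% |
| Detectable OR, 57 per group | 4.04 | 3.18 | 2.93 | 2.90 | 3.02 | 3.35 | 4.15 |

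With 36 per group, 80% is exceeded for control rates of about 18.5-51%. With 57, it is reached for about 9-71%.

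**Step 5: the planned test.** Section 9.4.2 specifies a mixed-model treatment × time contrast, not a post-intervention two-proportion test. A rough change-score simulation (equal baseline rates, control 20-50%) gave at most about 41% at 20 per group with OR 4.4, and at most about 61% at 36 per group with OR 4.3. The planned contrast does not rescue the 10-20 figure.

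**The case against.** The strongest reply is that the 10-20 claim and the standalone-trials claim belong to calculations that V14 revised. V14 repeats the odds ratios, drops the 10-20 clause and substitutes 72, so the difference is a revision and not a contradiction. Neither legacy claim set the sample size: the original plan used 40 per group, and V12 kept 120 dyads overall. Much of this stands. But both statements remain in the body of the current section 9.2, not in the amendment history, and nothing there withdraws them. They were also wrong when written.

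The stated range is not wrong at every point either: 20 per group at OR 8.7 does exceed 80% for control rates of about 10-50%. That also stands. On the natural pairing, though (20 with OR 4.4, 10 with OR 8.7), both ends fail.

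Three stronger readings are tempting and are not supported.

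- *A null result from a 16-per-arm comparison could be misread.* Section 9.4.2 calls the V14 analysis similar to V12's, which analysed the trials separately. But sections 4.2 and 9.2 remove the in-person arm, and the V14 analysis text names only SPIRIT-remote against usual care with site as a fixed effect. No 16-per-arm test remains.
- *V14's 72 dyads are wrong.* They are not. The figure holds over a plausible span of control rates; it is conditional on a rate that is not given.
- *The trial is underpowered at 120 dyads.* The detectable odds ratio at 57 per group is below 4.3 at every control rate from 10% to 70%. The change-score simulation gave less at 60 per group (72-81% with almost no between-dyad variation, 45-48% at a random-intercept SD of 3). It is not the planned model, though, and with a large SD a conditional OR of 4.3 is a much smaller marginal effect: at SD 3, simulated rates of 50% and 66% give an OR of 0.66/0.34 = 1.94. The documents give no within-dyad correlation with which to settle it.

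**Conclusion.** The point holds as an error in stated figures, not as a defect in the trial's size. At OR 4.4, 20 per group cannot exceed 62% power (74% one-sided), and 10 per group at OR 8.7 cannot exceed 61%. These ceilings need no assumption about the control rate, only the two-proportion test at 0.05. The V12 adequacy statement is wrong for the 3-arm trial, by about 28 percentage points at best (80 − 52), in a design no longer in use.

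V14's 72-dyad figure cannot be verified as written: it is right for control congruence of about 18.5-51% and wrong outside that range. The 120-dyad target is not undermined on the two-proportion approximation with the assumed 3.8% attrition. That last statement is about a post-intervention comparison and does not carry over automatically to the treatment × time contrast.

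**What to change.** All changes are to the text of section 9.2.

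1. Delete both occurrences of the 10-20 claim and the V12 adequacy statement for the standalone trials. Alternatively, restate them as about 31-50 dyads per group for OR 4.4 and 15-25 for OR 8.7, for control congruence of 10-60%, and give at most about 52% power at OR 4.4 for the 16-per-arm trial.
2. In the V14 paragraph, state the assumed control congruence, alpha, sidedness, test and attrition. Reconcile the odds ratio of 4.3, called the smallest, with the range starting at 4.4.
3. Give power, or the detectable odds ratio, for the 120 dyads planned: about 2.9-4.2 for control rates of 10-70% at 57 per group. Label it as a post-intervention two-proportion approximation to the planned mixed-model contrast.

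The cost is a short edit. The 120-dyad target, design and analysis do not change. Some stated figures become less favourable.

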9.3 POPULATIONS FOR ANALYSES

Patient-surrogate dyads will be the primary unit of analysis; all analyses will be intent to treat with all available data from all participants.

9.4 STATISTICAL ANALYSES

9.4.1 GENERAL APPROACH

Analyses will be intent to treat with all available data from all participants. Preliminary analyses will include summarizing variables with descriptive statistics and graphical displays or frequency tables. Distributional assumptions will be assessed and the data transformed as necessary. Baseline characteristics will be examined to explore possible between-group differences using analysis of variance and chi-square tests as appropriate. We will investigate missing data with pattern analysis for data missing at random or missing not at random, and use maximum likelihood or multiple imputation appropriate for each type to impute missing values. We will conduct sensitivity analyses to encompass different scenarios of assumptions and evaluate consistency or discrepancy among them.

9.4.2 ANALYSIS OF THE PRIMARY ENDPOINT(S)

SPIRIT effects on the preparedness outcomes: For dyad congruence, a binary outcome (congruent or not congruent), a generalized mixed effects logistic regression model will be used. Specifically, a random intercept model will be used to account for dyad level variation over time while treatment group, time (baseline and post-intervention), and treatment x time interaction will be treated as fixed effects. If there is a significant treatment x time interaction ($\alpha<0.05$) (an overall treatment effect), then two contrasts will be tested for individual treatment effectiveness (usual care vs SPIRIT-in person and usual care vs SPIRIT-remote). Adjustments for multiple pairwise comparisons will be made using Tukey's test. Surrogate DMC and preparedness scores, we will use linear mixed

effects regression models, adjusting for potential covariates as appropriate. Since this is not a non-inferiority trial where two or more interventions that have been proven to be superior to usual care are being compared, the contrast, SPIRIT-in person vs SPIRIT-remote, cannot be tested. However, if superiority of the two modalities to usual care is determined, the estimated group differences could be used for selecting a non-inferiority margin or equivalence range^{124,125} for future studies.

In light of the changes in study design (V12), we will update the statistical analysis plan. In particular, the preparedness outcomes from the 2-arm and 3-arm RCTs will be analyzed individually to evaluate the effect of the interventions. We will use mixed effects models as mentioned above and use contrasts to compare between the three and two intervention groups respectively. In addition to separate analyses, we will conduct pooled analysis by using analysis of variance methods (ANOVA) and incorporating an indicator variable for study and evaluate the (study x intervention group) interaction effect. We will also explore a meta-analysis approach to obtain a common intervention effect of SPIRIT-remote vs usual-care, from the two studies. If the effect sizes obtained from the individual studies are relatively homogeneous, their individual results may be combined to produce an estimate of the intervention effect. A weighted pooled estimate of effect size can be obtained, using the inverse of each study's variance as the weight. Because the studies are almost identical, we anticipate the variance to be fairly similar in both cases; a fixed effects approach will be used to estimate the variance.

With revision V14: The revised statistical analysis plan will be similar to that described in V12. Our primary aim will be to evaluate the effect of the SPIRIT- remote intervention group versus usual care on the outcomes of interest. We will use generalized linear mixed effect modeling and compare changes in treatment group means or proportions over time using contrasts. Because we only have 3 clusters (sites), fitting a multilevel model would not be feasible. We will instead adjust for site as a fixed effect in our mixed effects model. We will also compare our findings to those from Stage 1A to assess any substantial difference in effect sizes.

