Because adult day care programs and other community organizations are social services, they typically may not keep health records. In the cases where a dementia diagnosis cannot be confirmed from reliable sources, study staff will administer screening questions and a valid questionnaire, "Short Form of the Informant Questionnaire on Cognitive Decline in the Elderly (Short IQCODE)", to the family caregiver to determine whether a patient's cognitive impairment is likely dementia or due to other neurodegenerative condition. The initial screening questions will consist of the following questions:

- Has your loved one been evaluated for memory problems at the doctor's office?
 - If yes, what was the formal diagnosis at that time?
 - Do you have any test results related to the diagnosis?
- Does your loved one take any cognition- enhancing drugs, such as Aricept, Exelon, Reminyl, Namenda, or Provigil?
- Has your loved one had a stroke before this memory problem?

If a caregiver reports their loved one as having dementia based on the screening question and IQCODE (a score 3.3 or higher), study staff will schedule a meeting to determine full eligibility of their loved one and consent.

For all recruitment sites, the location for consent meeting can be flexible to meet the demands of participants.

Retention strategies:

Stage 1A (pre-testing)

Subject participation will last about three weeks. Each member of the dyad will receive a \$30 gift card at completion of the post-intervention follow-up (Ideally 2-3 days after the intervention session).

Stage 1B (formal pilot testing)

To Maximize Participant Retention, strategies found effective in retaining dyads over 12 months (dropouts, 3.8%) in our efficacy trial³⁰ will be used: (a) obtain backup contact information, (b) make confirmation phone calls 2 days prior to each appointment, (c) make scripted monthly check-in calls, (d) send holiday and special occasion cards, (e) assign the same data collector whenever possible, (f) compensate each member of the dyad as a token of appreciation (\$20 at baseline, \$25 at post-intervention assessment) and surrogates who complete the 1-year follow-up interview (\$30 at 12 months); and (g) use a cell phone matched to the participant's wireless network provider whenever possible (so that their minutes do not run out).

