- We will also assess the **overall preparedness for end-of-life decision making** using the 26-item investigator-developed measure. The measure assesses the level of preparedness for end-of-life decision making in the cognitive, emotional, and behavioral dimensions on a 4-point scale (4=strongly agree to 1=strongly disagree) with higher scores indicating higher levels of preparedness. Patient and surrogate each will complete this measure separately.

In Stage 1B,

Acceptability. Patient and surrogate acceptability will be assessed using the 10-item ACP Acceptability Questionnaire developed from our previous trial.²⁴ Participants are asked how strongly they agree or disagree (4 to 1) with statements about their experience with SPIRIT sessions, including duration, interactions with the interventionist, level of comfort and satisfaction. Higher scores indicate greater acceptability. Each patient and surrogate will complete this survey following the preparedness outcome measures after the intervention.

Preparedness for end-of-life decision making (measured at baseline and ideally 2-3 days after the intervention or randomization):

- **Dyad congruence** will be assessed using the Goals-of-Care Tool,^{28,30} which has been modified to include two scenarios relevant to the context of AD. In the first, the patient has progressed to advanced dementia and develops a severe infection and is admitted to a hospital; the medical team believes recovery unlikely and continuing life-sustaining treatment would no longer be beneficial. There are three response options: “The goals of care should focus on delaying my death no matter what, and thus I want to continue life-sustaining treatment”, “The goals of care should focus on my comfort and peace, and thus I do not want life-sustaining treatment”, and “I am not sure”. In the second scenario, the patient has progressed to advanced dementia and develops a severe infection. The nursing home staff is asking whether the patient should be taken to an ED, which will lead to hospitalization with life-sustaining treatments. Patients and surrogates complete this tool independently and their responses are then compared to determine dyad congruence -- either congruent in both scenarios or incongruent. If both members of the dyad endorse “I am not sure”, they are considered incongruent.

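### The hypotheses are post-intervention differences, but 9.4.2 tests the difference in change with baseline left free; equating the arms at baseline would add about 3 to 11 power points at 120 dyads (assumed correlation 0.3 to 0.5, control congruence 0.3 to 0.5)

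*Combined protocol and SAP*

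**What the plan says.** Section 9.1 (Stage 1B) puts the congruence hypothesis as a difference at follow-up: "The number of intervention dyads who are congruent on goals of care at post-intervention will be significantly higher than that of control dyads". The hypotheses for surrogate decision-making confidence (DMC) and surrogate preparedness have the same form.

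Section 9.4.2 describes a random-intercept logistic model for congruence in which treatment group, time (baseline and post-intervention) and "treatment x time interaction will be treated as fixed effects"; the interaction is the test of the treatment effect. DMC and preparedness get linear mixed models with covariates to be chosen. V14 says the plan stays similar, adds site as a fixed effect, and describes the comparison as: "We will use generalized linear mixed effect modeling and compare changes in treatment group means or proportions over time using contrasts". Nowhere are the arms held to a common baseline mean, and the baseline value of the outcome is not named as a covariate.

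Section 9.2 (V14) claims more than 80% power with 72 dyads at an odds ratio of 4.3, and adds: "Considering attrition, the target sample size of 120 dyads will achieve sufficient power". For DMC, "our goal will be to establish the population parameters". Section 6.3 has the allocation envelope opened right after the baseline assessment, with V14 randomisation stratified by race within site. Section 2.2 reports that the team's full-scale trial in end-stage renal disease was analysed with adjustment for baseline values.

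**The concern.** Because randomisation follows baseline, the expected baseline difference between arms is zero. A model with a free treatment main effect estimates that difference anyway, and its sampling error passes into the change contrast. Using the known equality removes the error.

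Three things are at stake. The first is power for congruence. The second is interval width for DMC, where section 9.2 makes estimation the goal. The third is whether the power statement describes the planned test at all, since section 9.2 gives no test, control congruence rate, within-dyad correlation or sidedness. In addition, race is a randomisation stratum but is not named in the congruence model; for the two scale outcomes it could enter only as one of the unspecified covariates.

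**Working it through.** **Inputs from the documents.** Odds ratio 4.3; 72 dyads in the power statement (36 per arm); target 120; alpha 0.05. Section 5.5 cites 3.8% dropout in the earlier trial, so 120 × 0.962 / 2 = 57.7 per arm. I use 57 (120 less 5%, halved).

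**Assumed, because not given.** Two-sided test; control congruence p_C from 0.2 to 0.6, the same at baseline and follow-up; control-arm baseline-to-follow-up correlation (phi) of 0.1, 0.3 or 0.5, with the same latent correlation in the SPIRIT arm. SPIRIT-arm phi is then 0.08-0.11, 0.24-0.28 and 0.39-0.41, all below the feasible maximum of 1/√4.3 = 0.482.

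**Step 1: the plan's own figure.** With p_T = 4.3p_C / (1 − p_C + 4.3p_C), for example 1.29/1.99 = 0.648 at p_C = 0.3, a two-proportion test on follow-up alone at 36 per arm has power 82%, 86%, 85%, 81% and 73% at p_C = 0.2, 0.3, 0.4, 0.5 and 0.6. So the claim of more than 80% reproduces as a post-only comparison for p_C of about 0.2 to 0.5. That the sponsor used this test is an inference.

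**Step 2: approximate effect of the choice of test.** Relative to a post-only comparison, the variance factor is 2(1 − ρ) for the change contrast and 1 − ρ² with baseline equated. Take 80% at 72 dyads as post-only: z = 1.960 + 0.842 = 2.802. At 120 dyads, z = 2.802 × √(120/72) = 3.617.

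- ρ = 0.3: change 3.617/√1.4 = 3.057, power 86.4%; equated 3.617/√0.91 = 3.792, power 96.6%. Gain 10.3 points.
- ρ = 0.5: change 3.617/√1.0 = 3.617, power 95.1%; equated 3.617/√0.75 = 4.177, power 98.7%. Gain 3.5 points.
- At 115 dyads (about 4% dropout) the gains are 11.1 and 4.0 points.
- At ρ = 0.7 and 120 dyads the gain is only 0.2 points.

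The same approximation puts the change contrast at 65.8% with 72 dyads and ρ = 0.3.

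**Step 3: simulation of the planned model.** Random-intercept logistic regression, likelihood-ratio tests, 2,000 replicates per cell (standard error at most 0.011), 57 per arm:

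| phi | Test | p_C 0.2 | 0.3 | 0.4 | 0.5 | 0.6 |
|---|---|---|---|---|---|---|
| 0.1 | planned | 0.686 | 0.797 | 0.804 | 0.781 | 0.748 |
| 0.1 | equated | 0.954 | 0.967 | 0.966 | 0.946 | 0.912 |
| 0.3 | planned | 0.808 | 0.879 | 0.878 | 0.868 | 0.800 |
| 0.3 | equated | 0.959 | 0.985 | 0.978 | 0.964 | 0.933 |
| 0.5 | planned | 0.924 | 0.949 | 0.960 | 0.939 | 0.911 |
| 0.5 | equated | 0.987 | 0.993 | 0.993 | 0.983 | 0.965 |

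For p_C of 0.3 to 0.5 the gains are 16-17 points at phi 0.1, 10-11 at 0.3 and 3-4 at 0.5. Logistic regression of follow-up on baseline is within 0.003 of the equated model. Null rejection is 0.045-0.058 for the planned test and 0.045-0.059 for the equated one.

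At 36 per arm and p_C of 0.3 to 0.5, the planned test has 57-61%, 68-72% and 79-82% power at phi 0.1, 0.3 and 0.5; equated, 82-86%, 84-89% and 90-93%. So the planned test reaches the 80% quoted for 72 dyads only at a correlation of about 0.5.

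**Step 4: scale outcomes.** With equal variances, the variance ratio of equated to change is (1 − ρ²) / [2(1 − ρ)] = (1 + ρ)/2. Intervals shrink by 1 − √0.65 = 19%, 1 − √0.75 = 13% and 1 − √0.85 = 8% at ρ = 0.3, 0.5 and 0.7. Equivalently, 114 analysed dyads are worth 114 × 2/(1 + ρ) = 175, 152 or 134 under the change contrast.

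**The case against.** The strongest reply is that nothing is broken. The planned test holds its error rate, targets the same effect on the scale outcomes, and at 57 per arm has at least 80% power in every simulated cell with phi 0.3 or 0.5. In a pilot of preliminary efficacy, treatment by time is a conventional choice. That stands, and it limits this to an efficiency and alignment point.

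Other points stand in part:

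- The free baseline term is explicit only for congruence. For DMC and preparedness it is inferred from the V14 sentence on changes in group means, which most naturally carries the same model over.
- The gain depends on the control rate. At p_C = 0.2 or 0.6 it is 13-15 points at phi 0.3 and 5-6 at phi 0.5, so the 3-11 range understates it there. It fades as correlation rises.
- At the plan's DMC effect of d = 0.02 there is almost no power to gain (0.1-0.2 points); the benefit is narrower intervals.
- The outcomes are "measured at baseline and ideally 2-3 days after the intervention or randomization", which makes a correlation as low as 0.1 unlikely. But SPIRIT sessions come about two weeks after baseline, so the interval is longer in that arm, and the equal latent correlation is a simplification.
- Section 7.2 allows dyads randomised to SPIRIT but untreated to be replaced, with no matching rule for controls. Used freely, that would weaken baseline equality. It would also disturb the change contrast, so it is no reason to prefer the planned test.

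**Conclusion.** The concern holds. Section 9.4.2 tests a difference in change with the arms free at baseline, while section 9.1 asks about the post-intervention difference and randomisation justifies a common baseline. For congruence at 57 per arm, odds ratio 4.3 and control rate 0.3 to 0.5, equating baseline adds 10-11 points at correlation 0.3 and 3-4 at 0.5. The 16-17 points at correlation 0.1 are an upper end. The planned test is valid and generally adequate at 120 dyads, so this should be changed but does not threaten the trial. The more general gain is precision: intervals 8-19% narrower on the scale outcomes over correlations of 0.7 down to 0.3, assuming equal variances. Control rate, correlation and sidedness are assumptions, because the documents give none of them.

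**What to change.** In section 9.4.2, make the primary analysis the mixed model with baseline means constrained equal across arms. This keeps all available data, as sections 9.3 and 9.4.1 require. The alternative is the post-intervention outcome adjusted for its baseline value, using the planned imputation; a complete-case version would drop dyads with a missing score. For congruence, state whether the target odds ratio is dyad-specific or conditional on baseline, since the two differ. Keep site and add race, so that the model matches the randomisation.

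In section 9.2, restate power for that test at 120 dyads less attrition, giving the assumed control congruence, within-dyad correlation and sidedness.

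The cost is rewording these two sections, with the IRB review that any amendment needs. Baseline scores, race and site are already collected.
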